## **3. SUMMARY OF STUDY PLAN**

**Study Plan:** This is a multi-center, phase IIA, single-arm ‘window of opportunity’ pilot study of 25 mg per day of exemestane for 21 to 42 days in patients undergoing hysterectomy for CAH/ EIN or low grade endometrial cancer (grade 1 or grade 2). Tissue from participant’s research endometrial biopsy will be used for pre-surgical biomarker analysis. The tissue obtained from surgical excision will be used for post-treatment biomarker analysis.

Study recruitment will occur in gynecology oncology clinics at participating institutions. A lead gynecologic oncology surgeon has been identified at each site. Up to 40 patients will be accrued for this pilot study. An age, disease and body mass index (BMI) matched historical comparator cohort will also be identified in order to compare changes in the primary outcome, Ki-67 expression between biopsy and surgical specimen in an untreated cohort.

For the U.S. based sites, prior to the baseline (pre-surgical) clinic visit, a pre-screening telephone contact will be completed to determine interest and basic eligibility for the study. If the participant gives verbal consent, study materials will be mailed to them. Materials will include a full study consent form to read through prior to their visit as well as 2 tampons (one to be inserted prior to the baseline (pre-surgical) clinic visit and other one as back up) and instructions for inserting the tampon (appendix D).

At the baseline (pre-surgical) clinic visit, participants will meet the study team to discuss and sign the informed consent form. The study team (including the research coordinator and the treating gynecologic oncologist) will review their medical history, conduct physical examination and review of concomitant medications. Participants will also have baseline laboratory tests. These tests include Complete Blood Count (CBC) with differential and platelets, Comprehensive Metabolic Panel (CMP), Estradiol, Progesterone and Follicle Stimulating Hormone (FSH) in all women 45-55 years old and in women 56-59 years old if they report less than 2 years of amenorrhea to confirm the post-menopausal status. Additionally,

blood will be drawn for exemestane pharmacokinetics. This research blood sample for exemestane pharmacokinetics will be destroyed if the participant does not qualify for the study.

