The study participants will be matched with a historical nonrandomized control group based on age ( $\pm$  5 years), disease type and BMI ( $>20-24$ ,  $25-30$ ,  $>30$ ). Historical samples (no more than 5 years old) will be identified through pathologic databases that exist at all participating sites. Medical records will be reviewed to ensure correct matching. The pre-surgical and post-surgical tissue samples, within 42 days of each other, will be obtained from each historical subject. All subjects will be de-identified. IHC analysis of Ki-67 expression will be performed on the pre-surgical and post-surgical samples.

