4.1.2 No prior treatment for CAH/EIN/EC

4.1.3 Age  $\geq 45$  years

4.1.4 Post-menopausal confirmed with one the following criteria:

- $\geq 60$  years of age
- age 56 to 59 years of age with  **$\geq 2$  years** of amenorrhea
- age 56 to 59 years of age with **< 2 years** of amenorrhea and FSH within institutional post-menopausal range.
- age 45 to 55 years of age with FSH within institutional post-menopausal range.

The Ki-67 expression changes based on menopausal status and specifically varies based on what phase of the menstrual cycle the sample is collected. Therefore, in order to eliminate this source of variability, only postmenopausal women will be included in this trial. In addition, exemestane is currently approved for use in post-menopausal women only.

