## 4.2 Exclusion Criteria

**Criteria for Exclusion:** Participants will be excluded from the study for the following reasons:

- 4.2.1 Participants who had curatively treated invasive malignancies for which all treatments ended within 1 year prior to the study (with the exception of basal cell or squamous cell carcinoma of the skin),
- 4.2.2 Not a surgical candidate or surgery is not scheduled within 43 days from starting the study drug.
- 4.2.3 Receiving any other investigational agents.
- 4.2.4 Any gastrointestinal condition causing malabsorption or obstruction (e.g. celiac sprue, gastric bypass surgery, strictures, adhesions, history of small bowel resection, blind loop syndrome).
- 4.2.5 Has been on any hormonal treatment (including progestin-containing IUD) for CAH/EIN or low grade (grade 1 or grade 2) endometrial carcinoma in last 3 months.
- 4.2.6 Use hormone replacement therapy (including systemic or topical estrogen, progesterone, or testosterone based medication) or/and phytoestrogen supplements (i.e. black cohosh) or has been on progestin (including progestin containing IUD), tamoxifen or aromatase inhibitor within the prior 3 months.
- 4.2.7 Concomitant use of strong CYP3A4 inducers such as rifampicin, phenytoin, carbamazepine, phenobarbital or St. John's wort as these may significantly reduce the availability of exemestane.
- 4.2.8 Known hypersensitivity to exemestane or its excipients.
- 4.2.9 Known intercurrent illness or psychiatric illness/social situations that will limit compliance with study requirements.
- 4.2.10 Evidence or high suspicion of metastatic disease at enrollment.
- 4.2.11 Women with severe bone density issues/osteoporosis (defined as any medical treatment for osteoporosis, and/or a T-score of -2.5 or lower, and/or history of fracture of the hip or spine).
- 4.2.12 Unwilling or unable to undergo research biopsy during the baseline (pre-surgical) clinic visit, or inadequate research biopsy obtained during the baseline (pre-surgical) clinic visit (determined by the gynecologic oncologist at the time of the subject's pelvic exam).

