### **8.2.7 Comparison of Ki-67 expression changes between subjects and a historical cohort**

The reason a historic cohort will be studied is to provide the context in which to assess the effects of exemestane in reducing Ki-67 from baseline to post-exposure to exemestane. Specifically, there may be a change in Ki-67 expression from pretreatment biopsy to final surgical specimen in the historical control cohort suggesting that time alone (between biopsy and surgery) or potentially differences in tissues

acquisition (biopsy versus surgical specimen) may have an impact on Ki-67 expression.

The study participants will be matched with a historical nonrandomized control group based on age (+/- 5 years), disease type and BMI (>20-24, 25-30, > 30). This control group will provide a reference for how Ki-67 may change based on time (specifically time between biopsy and surgery which has to be within 42 days) or differences in specimen collection (endometrial biopsies versus surgical specimen), independent of exemestane exposure.

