##### **10.1.1 Tissue samples**

Endometrial biopsy tissue sample at baseline (pre-surgical) clinic visit

- First pass will immediately go into formalin and within 24 hours a Formalin Fixed Paraffin Embedded (FFPE) block will be made. Blocks will be shipped on frozen ice packs to prevent melting of the FFPE block.
- Second pass will be placed in a stabilizing agent (AllProtect) and stored at 4°C and then shipped on frozen ice packs.

Hysterectomy Tumor tissue sample at surgery

- Section snap-frozen and stored at -70/-80°C. Remove up to 1x1x1 cm of tumor and cut in half. If there is not a visible lesion, select a random 1x1x1 cm area from the endometrium. This can section can be smaller if the pathology team needs to review more of the endometrium. The amount and location of removal of specimen is at the investigators clinical discretion. This should be snap frozen and shipped on dry ice.
- A portion of the formalin fixed paraffin embedded block, which was collected as standard of care per institutional pathology guidelines, will be sent to the University of Minnesota and cut into 10 unstained 5µm slides. If the FFPE block cannot be sent due to limited amount of tumor, then 10 unstained 5µm slides will be cut and the slides will be shipped to UMN. Blocks will be shipped on ice to prevent melting of the paraffin.

Historical matched controls from repository:

- Identify a list of potential matched controls from the repository for each site that will satisfy the matching criteria mentioned in section 3 of the protocol.
- For each matched control, two samples will be collected, first from the pre-surgical biopsy remnant tissue and the second from the surgical tissue. This tissue can be sent as a block or cut into 10 unstained 5µm slides.
- All blocks or slides will be shipped at the end of study.
- If slides are sent, they should NOT be cut until the time of shipment.

Tissue analysis will be performed at the University of Minnesota (UMN) as detailed below. Specimens from the University of Wisconsin and University of Alabama will be shipped by an overnight carrier to the Biorepository laboratory at the University of Minnesota:

Biorepository & Laboratory Services  
Attn: [name]  
[name]  
[name]  
[name]  
[name]

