### **13.2 Randomization/Stratification**

In the absence of randomized placebo controls, we will obtain age, disease and BMI matched comparator cohort from each institution’s biobank. The historical samples from each matched control will need to be obtained within 42 days of each other in order to be consistent with the study participants. This matching will be one-to-one. A comparison of Ki-67 expression between subjects on this study and historic controls is not a primary goal of the study. The primary outcome is the overall change in Ki-67 expression between pre and post-treatment of each subject. The reason a historic cohort will be studied is to provide the context in which to assess the effects of exemestane in reducing Ki-67 from baseline to post-exposure to

exemestane. Specifically, there may be a change in Ki-67 expression from pretreatment biopsy to final surgical specimen in the historical control cohort suggesting that time alone (between biopsy and surgery) or potentially differences in tissues acquisition (biopsy versus surgical specimen) may have an impact on Ki-67 expression.

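### Historical controls need not be postmenopausal or clearly free of recent hormone use, as participants must be, which weakens the secondary Ki-67 comparison

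*Combined protocol and SAP*

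**What the plan says.** **Controls.** Section 3 sets the rule, which section 8.2.7 repeats: "The study participants will be matched with a historical nonrandomized control group based on age" (±5 years), disease type and BMI class. Section 13.2 gives the same three variables ("we will obtain age, disease and BMI matched comparator cohort from each institution’s biobank") and makes the matching one-to-one. The other limits are samples no more than 5 years old (section 3) and biopsy and surgical tissue within 42 days of each other (sections 3, 8.2.7 and 13.2). Section 10.1.1 tells sites to list repository controls that "will satisfy the matching criteria mentioned in section 3 of the protocol". In section 3 the medical-record review serves to confirm the matching. The one phrase on treatment is in section 3, which describes the comparison as one of "Ki-67 expression between biopsy and surgical specimen in an untreated cohort". The word is not defined, and it is not among the criteria that section 10.1.1 sends sites to.

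**Participants.** Section 4.1.4 says that Ki-67 depends on menopausal status and cycle phase, and continues: "Therefore, in order to eliminate this source of variability, only postmenopausal women will be included in this trial". Women aged 45-55 need an FSH in the postmenopausal range. Section 4.2.5 bars hormonal treatment of the lesion in the last 3 months. Section 4.2.6 bars hormone replacement and phytoestrogen supplements, and any woman who takes "or has been on progestin (including progestin containing IUD), tamoxifen or aromatase inhibitor within the prior 3 months".

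**Use of the controls.** Objective 8 and section 13.4 set the participants' Ki-67 change against the controls' change. Section 13.2 says this is not a primary goal.

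**The concern.** The protocol names a source of Ki-67 variability, removes it from the treated group by eligibility, and leaves it open in the group that is meant to show how Ki-67 moves without exemestane. A site that follows section 10.1.1 to the letter could supply a cycling woman, or one whose hormone use changed between biopsy and hysterectomy.

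The trial has a single arm, and its two specimens differ in time and in method of collection. The historical cohort is the only means of separating a drug effect from those two influences. Cycling controls add movement that participants cannot have. Controls who start, stop or change a hormonal agent around the interval can shift the control mean either way, so a real fall could be hidden or a spurious one suggested.

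**Working it through.** **1. The plan's own figures.** Section 13.4 uses a one-sided one-sample t-test at 0.05 with n = 30 and SD 7.5. The noncentral t distribution (29 df) gives detectable effect sizes of 0.465, 0.501 and 0.547 at power 0.80, 0.85 and 0.90. Multiplied by 7.5 these are 3.49, 3.76 and 4.10 points, against 3.5, 3.8 and 4.1 in the plan. For subgroups of 15 the range is 5.07 to 5.97, against 5.1-6.0. All reproduce, and none uses the controls. The documents give no power calculation for the historical comparison.

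**2. The two selection rules side by side.**

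| Item | Participants | Controls |
|---|---|---|
| Age | 45 or over (4.1.3) | within 5 years of the participant |
| Menopause | required; FSH needed at 45-55 (4.1.4) | no condition |
| Hormonal treatment of the lesion | barred, last 3 months (4.2.5) | *untreated*, undefined (section 3) |
| HRT, tamoxifen, aromatase inhibitor, progestin for other reasons | barred (4.2.6) | no clear condition |

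**3. Ages reached.** 45 − 5 = 40, so the rule reaches below the trial's own age floor. 60 − 5 = 55, so any participant aged 60 or under may receive a control aged 55 or younger, the range in which section 4.1.4 does not accept menopause without FSH. For participants well over 60 the exposure is small.

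**4. Added noise.** Inputs: 30 treated women, 30 controls (Schema) and SD of change 7.5 (section 13.4), here assumed for treated women and postmenopausal controls alike. The share p of cycling controls and their SD s are assumptions. Equal means in the two kinds of control and an unpaired comparison are also assumed.

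- Control variance = (1 − p) × 56.25 + p × s².
- Baseline SE of the difference = √[(56.25 + 56.25)/30] = √3.75 = 1.94.
- Inflation = √[(56.25 + control variance)/112.5].

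| s | p = 10% | p = 20% |
|---|---|---|
| 10 | √(116.875/112.5) = 1.02 | √(121.25/112.5) = 1.04 |
| 15 | √(129.375/112.5) = 1.07 | √(146.25/112.5) = 1.14 |
| 20 | √(146.875/112.5) = 1.14 | √(181.25/112.5) = 1.27 |

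At s = 20 the SE of the difference goes from 1.94 to 2.21 (p = 10%) or 2.46 (p = 20%).

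**5. Bias.** If k of 30 controls have a mean change that differs by d points from the rest, the control mean moves by (k/30) × d. For k = 3 to 9 and d = 2.5 to 10 (assumed), this runs from (3/30) × 2.5 = 0.25 to (9/30) × 10 = 3.0 points. With no drug effect and the shift toward a rise in controls, an unpaired one-sided 0.05 test of 30 against 30 (SD 7.5 in both) would reject about 6.5% to 45% of the time. A shift the other way would hide a drug effect of the same size.

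**6. Which hormone exposure matters.** The measure is change from biopsy to surgery. Exposure that is stable across both specimens moves both values and largely cancels. Exposure that starts, stops or is still taking effect around the interval does not.

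**The case against.** The strongest reply is that the comparison is declared secondary and contextual, and that *untreated* on a plain reading already excludes a woman given progestin for her lesion between biopsy and surgery. Both points stand. They narrow the matter to menopausal status and to hormonal agents taken for other reasons, where the text sets no clear rule. Section 10.1 also points to a lab manual for more detailed instructions. It is not available here and might hold further criteria, although section 10.1.1 itself refers sites to section 3.

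A reader might draw stronger conclusions that the documents do not support:

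- **The primary result is compromised.** It is not: that test uses no controls.
- **Precision falls by 27-49%.** That is the rise in the SE of the control mean alone (1.37 to 1.74-2.04, with s = 20). For the planned difference it is 14-27% on the same assumptions.
- **A progestin-induced fall of some 20 points would mask the drug.** No figure supports this. Section 13.4 quotes a mean decrease of 7.2 on letrozole. Section 8.2.2 puts average regression on progesterone at about 6 months, against a gap of at most 42 days. Regression is not Ki-67, but nothing points to 20.
- **Every control aged 55 or younger is cycling.** The rule permits such controls; the documents do not say how many there would be.
- **About 2,000 archived cases are available.** Section 4.4 gives three sites' yearly figures of about 100 (Wisconsin's is 10 eligible a month), and these count patients seen. They do not count paired tissue that meets the matching, age and interval limits.

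**Conclusion.** The gap in the selection rule is established from the text. As written, the rule can admit controls whom the protocol's own reasoning would exclude from the treated group, and so yields a weaker comparator than the planned chart review could give. The consequence is confined to Objective 8 and the relative comparison in section 13.4. The primary test, its power and the sample size stand.

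The size cannot be fixed from the documents, which give neither a contamination rate nor an SD of change in cycling women. Over shares of 10-20% and SDs of 10-20, the SE of the difference rises between 2% and 27%, and bias depends wholly on the assumed shift. The change is worth making because the cohort is the only check of its kind in the trial.

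**What to change.** In sections 3, 8.2.7 and 10.1.1, add eligibility conditions for controls, to be checked in the record review already planned:

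1. **Postmenopausal on the chart**, using the categories of section 4.1.4. For women under 60 without a charted FSH, accept documented menopause or at least 2 years of amenorrhea. At 45-55 this is looser than the participant rule, but an archived chart may hold no FSH. If neither is documented, choose another control within the ±5-year band; do not widen the band.
2. **No charted use of the hormonal agents in 4.2.5 or 4.2.6** in the 3 months before the biopsy or between biopsy and surgery. State that this is what *untreated* means.
3. **Unknown status.** Record controls whose menopausal or hormone history cannot be established, and repeat the comparison without them.

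The conditions should be settled before sites draw up their lists, since control tissue ships at the end of the study and subjects are de-identified. The cost is protocol wording, two or more extra chart-review items per control, and fewer candidates for the youngest participants. No sample-size figure changes.

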#### **4. PARTICIPANT SELECTION**

In the U.S. based sites, whenever feasible, potential participants will be pre-screened for the study and contacted by the study team prior to their planned baseline (pre-surgical) clinic visit. The advantage of this is to introduce the study concept to the potential participant and allow her to place a tampon for specimen collection prior to her baseline (pre-surgical) clinic visit. If the participant gives verbal consent over the phone for the screening portion of the study, a pre-study packet will be mailed to her. This packet will

contain an informed consent form for her review and 2 commercially available tampons (one to be inserted in her vagina 8-12 hours before her baseline (pre-surgical) clinic visit and one for back up) along with instructions on how to insert a tampon (Appendix D). The tampon will be removed during the baseline (pre-surgical) clinic visit by the physician at the time of the pelvic exam. If the participant is eligible and agrees to take part in the study, the tampon will be processed and the resultant protein and DNA will serve as a pre-treatment sample. If the participant is either not eligible or refuses to sign the study consent, the tampon will be discarded. If a subject was unable to place a tampon prior to their baseline (pre-surgical) clinic visit, she will still be eligible for participation in this study.

**For EOG site only**, the patient will be approached for study participation when they first present with postmenopausal bleeding.

#### **4.1 Inclusion Criteria**

Eligible participants must meet the following requirements:

4.1.1 Females with a histologically proven CAH/ EIN or low grade (grade 1 or grade 2) endometrial carcinoma (EC) for which surgery is planned. The pathologic report from the referring facility will be used to determine pathologic eligibility. This report must be within 45 days of their baseline (pre-surgical) clinic visit.

4.1.2 No prior treatment for CAH/EIN/EC

4.1.3 Age  $\geq 45$  years

4.1.4 Post-menopausal confirmed with one the following criteria:

- $\geq 60$  years of age
- age 56 to 59 years of age with  **$\geq 2$  years** of amenorrhea
- age 56 to 59 years of age with **< 2 years** of amenorrhea and FSH within institutional post-menopausal range.
- age 45 to 55 years of age with FSH within institutional post-menopausal range.

The Ki-67 expression changes based on menopausal status and specifically varies based on what phase of the menstrual cycle the sample is collected. Therefore, in order to eliminate this source of variability, only postmenopausal women will be included in this trial. In addition, exemestane is currently approved for use in post-menopausal women only.

4.1.5 ECOG performance status  $\leq 1$  (appendix A)

4.1.6 Participants must have normal organ and marrow function as defined below:

- Hemoglobin  $\geq 9$  g/dL
- Serum creatinine  $\leq 1.5 \times$  upper limit of normal or calculated creatinine clearance  $\geq 60$  mL/min using Cockcroft-Gault equation for patients with creatinine levels  $> 1.5 \times$  Institutional ULN
- Total bilirubin  $\leq 1.5 \times$  ULN OR direct bilirubin  $\leq 1 \times$  ULN,
- AST and ALT  $\leq 2.5 \times$  ULN
- Hematologic function: WBC  $\geq 3000/\text{mcl}$ ;
- platelets  $\geq 100,000/\text{mcl}$ .

4.1.7 Able and willing to take oral medications.

4.1.8 Ability to understand and the willingness to sign a written informed consent document.

4.1.9 BMI > 20

## 4.2 Exclusion Criteria

**Criteria for Exclusion:** Participants will be excluded from the study for the following reasons:

- 4.2.1 Participants who had curatively treated invasive malignancies for which all treatments ended within 1 year prior to the study (with the exception of basal cell or squamous cell carcinoma of the skin),
- 4.2.2 Not a surgical candidate or surgery is not scheduled within 43 days from starting the study drug.
- 4.2.3 Receiving any other investigational agents.
- 4.2.4 Any gastrointestinal condition causing malabsorption or obstruction (e.g. celiac sprue, gastric bypass surgery, strictures, adhesions, history of small bowel resection, blind loop syndrome).
- 4.2.5 Has been on any hormonal treatment (including progestin-containing IUD) for CAH/EIN or low grade (grade 1 or grade 2) endometrial carcinoma in last 3 months.
- 4.2.6 Use hormone replacement therapy (including systemic or topical estrogen, progesterone, or testosterone based medication) or/and phytoestrogen supplements (i.e. black cohosh) or has been on progestin (including progestin containing IUD), tamoxifen or aromatase inhibitor within the prior 3 months.
- 4.2.7 Concomitant use of strong CYP3A4 inducers such as rifampicin, phenytoin, carbamazepine, phenobarbital or St. John's wort as these may significantly reduce the availability of exemestane.
- 4.2.8 Known hypersensitivity to exemestane or its excipients.
- 4.2.9 Known intercurrent illness or psychiatric illness/social situations that will limit compliance with study requirements.
- 4.2.10 Evidence or high suspicion of metastatic disease at enrollment.
- 4.2.11 Women with severe bone density issues/osteoporosis (defined as any medical treatment for osteoporosis, and/or a T-score of -2.5 or lower, and/or history of fracture of the hip or spine).
- 4.2.12 Unwilling or unable to undergo research biopsy during the baseline (pre-surgical) clinic visit, or inadequate research biopsy obtained during the baseline (pre-surgical) clinic visit (determined by the gynecologic oncologist at the time of the subject's pelvic exam).

